1. INTRODUCTION

This statistical analysis plan (SAP) provides a framework and guidelines for the statistical analysis of the Children and Young People's Health Partnership (CYPHP) randomised controlled trial for presentation, reporting and publication. Any deviations from the statistical analysis plan will be documented in the statistical end of trial report.

1.1 Trial design - Background and Rationale

Lambeth and Southwark have high levels of deprivation. These boroughs have higher than national average rates of child mortality and high unplanned health service use, and rising hospital outpatient use for children and young people (CYP) with long term conditions (LTC). The local Clinical Commissioning Groups (CCGs), Local Authorities, and Healthcare Providers have attempted to address these problems by forming The Child and Young People's Health Partnership (CYPHP) and together implementing a new model of integrated healthcare across the two boroughs. The CYPHP model aims to deliver more effective, coordinated care in primary care and community settings, and promote better self-management for CYP with common health complaints and LTCs. The CYPHP model is designed as a large-scale quality improvement initiative implementing integrated care pathways for children, for example across service provider organisations and professional groups.

This cross-organisational, system-wide, transformative, and academically rigorous approach to improving child health services aims to deliver care to traditionally hard to reach groups.

The intention of the Partnership is to roll out the full CYPHP Evelina London model of care across Lambeth and Southwark. However, due to resource limitations, implementation will occur in phases. In the first phase (~two years), approximately half of GP practices across the boroughs will implement the CYPHP model while others will offer enhanced usual care (EUC). It is expected that all the EUC practices will also adopt the CYPHP model after two years, so that all of Lambeth and Southwark will eventually be using the CYPHP model. This phased roll-out schedule offers the unique opportunity for a rigorous evaluation of the CYPHP Evelina London model of care at scale, using an opportunistic cluster Randomised Controlled Trial (cRCT) design. The unit of randomisation is the "GP hub", a group of general practices who work together to share workloads, and where the GP – paediatrician co-located clinics occur. We term these GP hubs as clusters. During the first phase of roll-out, outcomes in the CYPHP model practices can be evaluated, while the EUC practices offer a natural comparator control group. Seventy GP practices across Lambeth and Southwark, grouped into 23 clusters, were randomised to provide either the CYPHP model of care (n=11) or enhanced usual care (n=12).

We hypothesise that the CYPHP Evelina model of care will improve the quality of care provided to children which will improve both children's health and reduce their health service use compared with patients from EUC practices.

1.2 Related work

This analysis plan is not a stand-alone piece of work but sits within a mixed method evaluation that incorporates both process and economic evaluations. The process and economic evaluation analysis plans are described in separate documents. There is also a detailed document on Data and reporting guidelines and a published study protocol.¹

2. PURPOSE OF THE EVALUATION

- To evaluate the impact of the Children and Young People's Health Partnership (CYPHP) Evelina London model of care on the health, healthcare, and health service use of children and young people (CYP).
- To understand how and why the CYPHP Evelina London model of care was effective or ineffective, and to identify contextually relevant strategies for successful implementation as well as practical difficulties in adoption, delivery and maintenance to inform wider implementation.
- To assess the costs of delivery and cost effectiveness of the CYPHP Evelina Model of care compared to enhanced usual care.
- To generate rigorous evidence for local, national and international service providers and commissioners and contribute to the evidence base in CYP health services research.

3. TRIAL EVALUATION OVERVIEW

This evaluation will address the above objectives using data about children aged 0-15 years (<16) registered with a GP practice in Southwark or Lambeth. The evaluation will take 3 levels.

1. A population evaluation (all children)
2. A tracer condition evaluation (all children identified as having or potentially having asthma, eczema, constipation)
3. a) A consented tracer condition evaluation (all children with asthma, eczema, or constipation who have consented for additional data collection and associated data linkage)
b) A consented tracer condition evaluation (all children with asthma, eczema, or constipation who have consented for additional data collection and associated data linkage) including only those who met the threshold to be offered CYPHP service(s).

4. INTERVENTION

The intervention is outlined in detail in the evaluation protocol. In brief, the CYPHP Evelina London model aims to provide comprehensive coordinated care for CYP through several mechanisms:

- Integrating primary and secondary healthcare
- Integrating physical and mental healthcare
- Integrating healthcare with public health
- Improving the age appropriateness of care.
- Providing tailored care that is responsive to patients' needs

During phased roll out and the evaluation trial, the CYPHP Evelina London model comprises two groups: 1) interventions that are being implemented across both arms of the trial, called "enhanced usual care" (EUC) and 2) The full CYPHP Evelina London model, comprising EUC plus additional interventions. Thus, EUC serves as the control arm, and the full CYPHP Evelina London model serves as the intervention arm.

4.1 Enhanced usual care (control arm)

All practices within Lambeth and Southwark will receive:

- Decision support tools for GPs comprising guidelines (in line with national evidence-based guidelines), algorithms, and referral guidance for common conditions such as constipation, eczema, urinary tract infection, enuresis, headache, and food allergies. They are in an electronic format, embedded into local GP data systems so that they can be accessed easily during a consultation.
- Paediatric hotline enabling rapid communication between GPs and paediatricians to discuss urgent support, management, or referral of an individual child or young person.
- School-based emotional resilience building and mental health first aid.
- Minor illness and wellness support and services for the most common problems and illnesses, to help parents and professionals to keep CYP well at home.
- CYPHP Health Checks for CYP with tracer conditions (asthma, epilepsy (service discontinued for epilepsy), eczema, constipation) and their parents – a condition-specific biopsychosocial questionnaire about disease or condition status, emotional wellbeing, and social factors. Information collected from the CYPHP Health Check is added to patients' GP records, and families are sent a summary of their scores on the questionnaires.
- CYPHP Health Packs following the Health Check, for CYP with tracer conditions, and their parents, comprising self-management support, health promotion, and health education material.

4.2 CYPHP Evelina London model (intervention arm)

In addition to the components of the EUC arm, the CYPHP Evelina London model comprises two types of clinical services:

Targeted care for CYP with ongoing (tracer) conditions

CYP with tracer conditions are eligible for a tailored clinical service delivered by the multidisciplinary CYPHP Health team in primary and community care settings and in patients' homes. Children are actively identified for the service using a call and recall system which interrogates their primary health care records for evidence of the condition from diagnosis, management or treatment, identifies CYP with a tracer condition, and invites the parent/carer to complete a CYPHP Health Check. Health Check responses are used to triage CYP based on clinical need. The length and intensity of intervention is left to the clinical judgement of the multi-disciplinary team delivering CYPHP services.

Universal care available for CYP with any condition.

CYP with any condition are eligible for “in-reach” CYPHP clinics. These clinics are integrated child health clinics jointly run by GPs and local “Patch Paediatricians” who are linked to a cluster of GP practices. Clinics are held in primary care settings. They offer generalist and specialist advice co-located and coordinated conveniently close to home for patients. In-reach clinics will typically be for CYP who would otherwise have been referred to hospital for an outpatient appointment with a general paediatrician.

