6.2 Secondary care clinical patient data

All hospital activity is recorded within the patient administrative system (PAS). The activity of interest to our evaluation is:

- Admitted patient care data
- A&E data
- Outpatient data

Agreements on sharing data have been made between CYPHP and the trusts in Lambeth and Southwark - Guy's and St Thomas's (GSTT) and King's College Hospital (KCH). We will receive quarterly extracts of health care activity at St Thomas's, Guy's or King's College Hospitals of

children registered with Lambeth and Southwark GP practices. Local coding (within St Thomas's, Guy's or King's College Hospitals) is completed within a month of a patient's health activity, with a freeze date of 6 weeks after the activity. This will mean the coding will be relatively stable and few changes will be made after 2 months of patients' activity/discharge.

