10.3 Outpatient appointment referrals from primary care

An outpatient appointment referral occurs when a primary care clinician decides a child needs specialist care. These referrals are recorded in EMIS as Read/SNOMED codes.

Outpatient appointment referral rates

The rate of Outpatient appointment referral rates will be measured as count per patient-year.

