10.3.2 Referral to General Paediatrics and Tertiary services related to the tracer conditions

Rationale: If CYPHP is improving health, or through offering early intervention for asthma/eczema/constipation, we hypothesize there will be fewer tertiary service referrals for these conditions, as well as fewer referrals to general paediatrics. Referrals related to the tracer conditions are defined in Appendix. This outcome will include the referrals to General Paediatrics (defined in 10.3.1), and in the terms relevant to tracer conditions, listed in Appendix. This outcome will be used for “Health Service Use Population-level population” (as defined in section 8.1).

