10.5.1 Attendance of General Paediatrics Outpatient appointment

These are defined using the terms in Appendix. This outcome will be used for the “Health Service Use Population-level population” (as defined in section 8.1).

10.5.2 Attendance of General Paediatrics Outpatient and Tertiary services related to the tracer conditions

Rationale: If CYPHP is improving health, or through offering early intervention for asthma/eczema/constipation, we hypothesize there will be fewer general paediatrics and tertiary service referrals for these conditions. These attendances are defined in Appendix. This outcome will be used for “Health Service Use Population-level population” (as defined in section 8.1).

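### In-reach clinics move paediatric visits out of hospital in one arm only, so a fall in hospital outpatient counts should not be read as better health or lower total use unless those visits are also counted

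*SAP*

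**What the plan says.** **The service.** SAP section 4.2 introduces the intervention arm with: "In addition to the components of the EUC arm, the CYPHP Evelina London model comprises two types of clinical services". One of the two is the in-reach clinic, run jointly by GPs and a paediatrician linked to a group of practices. On place: "Clinics are held in primary care settings". On whom it serves: "In-reach clinics will typically be for CYP who would otherwise have been referred to hospital for an outpatient appointment with a general paediatrician". Section 4.1 lists no such clinic for the control arm. The only other mention of in-reach is in section 5.3, as a reason for grouping practices.

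**The data.** Section 6 names three main sources: GP systems, hospital systems and questionnaires. For hospital activity, section 6.2 says: "We will receive quarterly extracts of health care activity at St Thomas's, Guy's or King's College Hospitals of" children registered with practices in the two boroughs.

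**The outcomes.** Section 10.3 defines a referral broadly: "An outpatient appointment referral occurs when a primary care clinician decides a child needs specialist care", recorded by codes in EMIS. Sections 10.3.1 and 10.5.1 count general-paediatric referrals and attendances. Sections 10.3.2 and 10.5.2 add tertiary services for the tracer conditions, and 10.3.4 and 10.5.4 count everything. The term lists are in the files cited in 23.9 and 23.10. Section 9.1 (item 8) and section 10.8 add outpatient attendances to non-elective admissions, as a rate and, in 10.8, also as a cost.

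**The expected reading.** Section 1.1 expects better care that will "improve both children's health and reduce their health service use compared with patients from EUC practices". Section 10.3.2 reasons: "If CYPHP is improving health, or through offering early intervention for asthma/eczema/constipation, we hypothesize there will be fewer tertiary service referrals for these conditions", and extends this to general paediatrics. Section 10.5.2 gives the same rationale for attendances.

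**The concern.** The in-reach clinic is itself a paediatric appointment, designed to replace a hospital one. A child seen there in an intervention hub does not appear in the hospital attendance extract. The same child in a control hub, referred to hospital and attending, does. The difference arises after randomisation from what is counted, so adjustment for the baseline rate and the other covariates in section 10.9 cannot remove it.

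What is at stake is the meaning of several secondary outcomes. The SAP hypothesises less service use and ties fewer referrals to better health or early intervention. Change of setting, which section 4.2 describes, is not mentioned as an explanation. A lower hospital count is compatible with the same number of children seeing a paediatrician and no change in their health. In the 10.8 cost summary, a relocated visit would appear as cost removed, because in-reach is not a listed activity.

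**Working it through.** **Step 1. Is in-reach counted anywhere?**

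- Attendances (10.5): the source is hospital activity (6.2), and the clinics are in primary care (4.2). No stated text adds them. This part is reasonably firm.
- Referrals (10.3): the definition is broad enough to cover a GP booking into an in-reach clinic, if it is coded in EMIS and if the term lists include the code. The visible text does not settle this.
- All referrals (10.3.4) and all attendances (10.5.4): the first is aimed at increases from unmet need, the second at unintended consequences. Neither adds in-reach contacts.
- Primary care consultations (10.2): in-reach visits may be counted here, depending on lists kept in separate files. This is a separate outcome mixed with ordinary GP and nurse contacts, so it cannot show how many visits moved.
- Combined rate and cost (9.1 item 8; 10.8): these carry outpatient attendances and so inherit the gap.

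**Step 2. Size under pure substitution.** Let s be the share of would-be general-paediatric visits that move in-reach, with need unchanged. For a general-paediatrics-only count, rate ratio = 1 − s:

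- s = 10%: 1 − 0.10 = 0.90
- s = 20%: 1 − 0.20 = 0.80
- s = 30%: 1 − 0.30 = 0.70

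Where general paediatrics makes up only a share g of a broader count (10.5.2, 10.5.4, the combined rate), the ratio is 1 − g·s, nearer to 1. The SAP gives neither s nor g.

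**Step 3. Could such a shift reach significance?** This is an illustration only. The unmatched cluster-rate formula is

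power = Φ( √{ (c − 1)(λ₀ − λ₁)² / [ (λ₀ + λ₁)/y + k²(λ₀² + λ₁²) ] } − 1.96 ).

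Inputs from the SAP: c = 11 clusters per arm and 3800 children per cluster (5.1); 2.25 years, April 2018 to June 2020 (8.1), so y = 3800 × 2.25 = 8550 person-years per cluster. Assumptions: outpatient rate λ₀ from 0.02 to 0.10 per patient-year; coefficient of variation k = 0.142 (stated in 5.1 for admissions, borrowed here) or 0.25.

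Example with λ₀ = 0.05, s = 20%, k = 0.142: λ₁ = 0.04; (0.09)/8550 = 0.0000105; 0.142² × (0.0025 + 0.0016) = 0.0000827; sum 0.0000932; √(10 × 0.0001/0.0000932) = 3.28; 3.28 − 1.96 = 1.32; Φ = 0.906.

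| Share moved | Rate ratio | Chance of a significant fall, k = 0.142 | k = 0.25 |
|---|---|---|---|
| 10% | 0.90 | 31–36% | 14–15% |
| 20% | 0.80 | 86–92% | 47–50% |
| 30% | 0.70 | over 99% | 84–87% |

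Section 7.1 ends the trial period a year later than 8.1. With 3.25 years, the 20% example rises only from 0.906 to 0.915. The SAP states no outpatient figure to reproduce.

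**The case against.** The strongest reply is that moving care out of hospital is an aim of the model. Section 1.1 names rising hospital outpatient use as a problem and wants care delivered in primary care and the community. A fall in hospital attendances is then a real effect and a legitimate outcome. This stands, and it is why the hospital-only outcomes should be kept. What does not follow is better health or lower total use.

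A reader might infer that the plan leaves in-reach out of every referral count. The documents do not support that: the 10.3 definition is broad and the term lists are not in the text.

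A reader might also infer that the shift can never be told apart from a true reduction. That goes too far. Consultations (10.2), the process evaluation (16), the per-protocol analyses (17) and the separate economic evaluation (1.2) all bear on interpretation, although none is stated to add in-reach to the outpatient count.

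Finally, 10.3.1 and 10.5.1 carry no health rationale of their own. The sentences in 10.3.2 and 10.5.2 are hypotheses, not rules for attributing a result, and the part quoted from 10.3.2 concerns tertiary referrals, which in-reach does not directly replace. This softens the charge. Both sections nevertheless extend the reasoning to general paediatrics, where substitution is expected.

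**Conclusion.** The point holds for hospital outpatient attendances in 10.5.1 and 10.5.2, in diluted form in 10.5.4, and for the combined rate and the 10.8 cost summary: each can fall through change of setting alone. For referrals in 10.3 it is conditional on EMIS coding and the term lists. Outcomes restricted to tertiary services are less exposed.

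The size is unknown. The ratio 1 − s applies only to general-paediatrics-only counts, and s is assumed throughout. The chances of significance also rest on assumed outpatient rates and on a borrowed or assumed coefficient of variation. They show that a moderate shift could matter, not that it will.

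It might be tempting to compare a 20% shift with the 20% reduction used for sample size in section 5.1. That figure belongs to non-elective admissions, a different outcome, which in-reach substitution does not directly affect. This is a cheap improvement to secondary outcomes and their interpretation, not a threat to the primary result.

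**What to change.** - Keep the hospital-only outcomes in 10.3 and 10.5, and label them as hospital use or shift in setting.
- State in both sections whether in-reach bookings and visits are included in the term lists.
- Add a secondary count to each section: hospital general-paediatric referral plus in-reach booking (10.3), and hospital general-paediatric attendance plus in-reach attendance (10.5). If the lists already include in-reach, count each contact once.
- Include in-reach visits at a unit cost in 10.8.
- Base any claim of reduced total paediatric outpatient use on the combined count.
- Do not add contacts with the CYPHP multidisciplinary team. They arise from active call and recall in the intervention arm and are not shown to replace referrals, so adding them would raise that arm's count by construction.

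**Cost:** some SAP wording and a small data join. The per-protocol analyses in section 17 already need records of engagement with the universal services, and section 6.5 provides a pseudonymised identifier for linkage. Section 6 does not list these records as a source, so the SAP should name them. The downside is that the apparent outpatient reduction may shrink.

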5. SAMPLE SIZE, RECRUITMENT, RANDOMISATION, AND BLINDING

5.1 Sample size and power

Population Evaluation

Pseudo-anonymised data from all children (<16 years) within participating practices will be used to analyse the impact of the CYPHP Evelina London model on health service use.

11 clusters in each arm, and an average of 3800 CYP per cluster, provides over 87% power to detect a reduction of 20% in the rate of non-elective admissions, assuming a coefficient of variation of 0.142, as explained below.

The number of CYP per cluster is estimated conservatively based on the 89382 CYP (age 0-15) registered in 2015 in the GP practices in the 23 randomised clusters. For each financial year 2013-14 – 2015-16, the baseline rate of non-elective admissions and the coefficient of variation was estimated using counts of non-elective admissions per cluster from financial years 2013-14 – 2015-16, and counts of CYP enrolled per cluster during 2013-2015. The coefficient of variation used in the sample size calculation was the mean of these three estimates. The rate of non-elective admissions was the total rate estimated by combining data from the three financial years.

Tracer Condition Evaluation

With 11 clusters in each study arm, the study team will need to recruit a minimum of 1006 CYP with a long-term tracer condition (asthma, constipation or eczema) per arm (total 2012). This number of participants will give the study 90% power to detect a mean minimum clinically important difference (MCID) of 4.5 points (standard deviation 16.5) in the primary child-health outcome tool (parental reported PEDSQL (Varni et al, 1999),² as used previously with children with chronic health conditions such as asthma (Varni et al, 2004).⁸ Intraclass coefficient (ICC) is assumed to be 0.02 based on study of quality of life in children and young people with a related condition, hay fever (Hammersley et al, 2010). Inter-cluster variation is assumed to be (0.03) based on the harmonic mean and variance of cluster size derived from GP registrations. This number also accounts for a 30% loss to follow up.

In total there are **23 clusters**, 12 in one arm and 11 in the other. As such the outlined sample size underestimates the total power as we have assumed 11 clusters in each arm.

5.2 Recruitment

The CYPHP Evelina London model of care is part of a service quality improvement initiative by a local partnership including service providers and commissioners of care, and is being implemented after extensive consultation and co-development with local stakeholders. Therefore, and in keeping with guidelines for the ethical conduct of cRCT's, patients within GP practices are being asked for their consent to participate in the follow-up evaluation, rather than consent for participation in a new model of care as this is part of a new standard service roll out. (Campbell et al, 2012)

OVERVIEW OF RECRUITMENT – TRACER CONDITION

- 1) **Providing service information for CYP and families.** Eligible patients with one of the three tracer conditions will be identified by their GP and receive text messages and a letter and information sheet outlining the new services being delivered in their GP practice. Potential participants are invited to contact the service, either by telephone or by logging onto a web page. The web page is a portal modelled on an existing and well-established platform in use for several years by another local programme (IMPARTS). It was adapted for use in CYPHP and tested for acceptability with local CYP and families.
- 2) **Inviting CYP and parents to participate in evaluation.** Parents of CYP receiving the service (either the CYPHP Evelina London model or EUC) for a tracer condition will be invited to participate in the evaluation, and provided with information sheets about the evaluation, in formats for the parent and child. These will be provided through the portal, in person, or by post.

3) **Informed consent/assent.** Those who would like to participate will be asked to give informed consent (using the web-based portal, in person, or by post) to participate in the evaluation and follow-up. Specifically, parents will be asked to:

- provide informed consent for the evaluation team to 1) access their child's clinical details including a baseline clinical screening questionnaire which is completed on entry into the clinical service, and 2) have access to, and link, the child's GP and hospital data to assess the impact of CYPHP on both primary and secondary health service use. The baseline clinical screening questionnaire, completed for clinical services, includes the Strengths and Difficulties Questionnaire, and a condition-specific questionnaire: Asthma Control Test, GSTT Symptom Severity Measure (for constipation), or Patient Oriented Eczema Measure.
- complete an evaluation questionnaire at baseline (including health related quality of life measured by PEDSQL and CHU9D, and parental wellbeing measured by the Warwick-Edinburgh Mental Wellbeing Scale), and complete the clinical screening questionnaire and evaluation questionnaire at 6-month, and annual follow-up.
- give informed consent to be contacted to potentially participate in qualitative studies evaluating the service

Patient information sheets will make it clear that parents can consent or refuse consent to any of these components. Participants will be free to withdraw consent without prejudice at any time.

A parent/carer alone or with their child may be involved in the recruitment process. If the CYP is under 12 years of age the parent/carer will be asked to provide, on behalf of the child, informed consent, if they are happy to take part in the evaluation. If the CYP is between 12 and 16 years of age, the parent will be asked to provide informed consent and if the CYP is available at the time when parental consent is requested, the CYP will be asked to provide assent if they wish to participate.

TRACER CONDITION RECRUITMENT TIMELINE

Recruitment began in April 2018. The first participant was consented 22MAY2018, following their Health Check 24APR2018. Recruitment is planned to complete in December 2020.

POPULATION EVALUATION DATA

The evaluation has data sharing agreements granting access to pseudo-anonymised data for all CYP under the age of 16 across the two boroughs for population level service-use analysis. Data in this pseudo-anonymised format are available from EMIS, a clinical records and informatics system used in primary care, and hospital administrative data. As individuals' data are provided in anonymized form (e.g. from administrative data sources or registries) to the research team for population-level evaluation, these CYP are not considered research participants (Weijer et al, 2012, p4), therefore individual consent is not required and as outlined in our ethics application and approval, Section 251 approval from the Confidential Advisory Group is not required.

